4.6 Discontinuation of Study Treatment, Withdrawal, and Compliance

Discontinuation from the study treatment does not mean discontinuation from the study. Subject will be considered in follow-up. Study procedures should still be completed as indicated by the study protocol, and AEs/SAEs will continue to be reported according to this protocol.

In the absence of treatment delays due to adverse events, study treatment/intervention may continue until:

- Disease progression.
- General or specific changes in the subject's condition renders the subject unacceptable for further treatment in the investigator's judgment.
- Intercurrent illness that prevents further treatment administration.
- Subject decides to withdraw from the study.
- The subject has significant noncompliance with the protocol (see below).
- Unacceptable adverse event(s) and/or dose-level reduction beyond requirements as detailed in this protocol.
- Study stopping rules are met.

Subjects who sign the informed consent form, enroll and receive the study intervention, but subsequently withdraw, or are withdrawn or discontinued from the study will not be replaced.

Consent Withdrawal

A subject may decide to withdraw from the study at any time. The MCWCC CTO will follow its IRB of record's SOPs regarding consent withdrawal.

If a subject intends on withdrawing consent, staff should confirm which of the following options the subject chooses and document the discussion:

- Full consent withdrawal, with no study follow-up.
- Selective consent withdrawal from interventional portion of the study but agrees to continued follow-up of associated clinical outcome information.

Investigator-initiated Withdrawal

The investigator will withdraw a subject whenever continued participation is no longer in the subject's best interests. Reasons for withdrawing a subject include, but are not limited to, disease progression, the occurrence of an adverse event or a concurrent illness, a subject's request to end participation, a subject's noncompliance or simply significant uncertainty on the part of the investigator that continued participation is prudent. The reason for study withdrawal and the date the subject was removed from the study must be documented.

4.7 Lost to Follow-up

The following actions must be taken if a participant fails to return to the clinic for a required study visit and/or is unable to be reached for follow-up:

- The investigator or designee must make every effort to regain contact and/or reschedule a missed visit with the participant.
- A participant is deemed lost to follow-up if his/her status cannot be obtained after all of the following occur at two consecutive scheduled protocol calendar timepoints:
 - Three telephone calls (at least one day apart) from the study team are unanswered,
 - AND**
 - A letter to the participant's last known mailing address goes unanswered,
 - AND**
 - These contact attempts must be documented in the participant's medical record or study file.
- Update OnCore® (follow-up tab and eCRF) when a participant is officially considered lost to follow-up.
- If a subject is considered lost to follow-up, but subsequently contacts the study team, the subject should be considered in follow-up again.

4.8 Accrual Suspension and Closure

The MCW PI facilitates the suspension and closing of accrual in the following manner:

- OnCore® tracks accrual throughout the study.
- If the study must be suspended, OnCore® is updated to a “suspended” status.
- When the accrual number is reached, OnCore® notifies staff of study closure.

4.9 End of Study Definition

A participant is considered to have completed the study if he or she completed all of its phases, including the last visit or the last scheduled procedure shown in the calendar of events, or has been discontinued.

4.10 Study Discontinuation and Closure

This study may be temporarily suspended or prematurely terminated if there is sufficient reasonable cause (as determined by the MCW study PI, DSMC, sponsor, and/or IRB). Written notification, documenting the reason for study suspension or termination, will be provided by the suspending or terminating party to study participants, investigator, funding agency, the Investigational New Drug (IND) sponsor and regulatory authorities. If the study is prematurely terminated or suspended, the MCW principal investigator (PI) will promptly inform the MCW Institutional Review Board (IRB), and the sponsor and will provide the reason(s) for the termination or suspension. Study participants will be contacted, as applicable, and be informed of changes.

5 TREATMENT PLAN

5.1 ATB Administration

ATB will be administered on an outpatient basis. ATB will be administered at a dose of 1,200 mg three times per day (roughly spaced every eight hours) as has been studied for ATB in

human oral leukoplakia trials and in esophageal cancer prevention trials. ATB may be taken with or without food.

| Regimen Description | | | | | | |
|---|-------------|----------------------------|--------------------------------|-------|----------|------------------------|
| ARMS | Study agent | Premedication; precautions | Dose | Route | Schedule | Duration |
| ARM 1 | ATB | None | 1,200 mg, Three times a day | Oral | Daily | 7-28 days ^a |
| a. Total duration depends upon scheduling of surgery. ATB administration must not exceed 28 days. | | | | | | |

- Patient must submit completed study diary to the study coordinator.

5.2 Supply

ATB

ATB will be produced by National Traditional Chinese Medicine Pharmaceutical Engineering Technology Research Center and shipped to MCW in the form of a tablet. ATB will be stored at room temperature in a cool place, free from excessive moisture and should be stable for two years. Analysis of pharmacokinetic properties is necessary before future efficacy trials can be initiated. We will examine an oral ATB dose of 1,200 mg, three times per day.

Study agents will be shipped to MCW in one batch. Study agent ordering contact information:

[name]
Department of Pharmacological and Pharmaceutical Sciences
College of Pharmacy
[name]
University of Houston
Houston, Texas 77204
Contact Information: [contact]

Each patient-specific bottle will be labeled by IDS pharmacy with the following:

- The study number;
- The bottle number (i.e., Bottle 1 of 2 and Bottle 2 of 2);
- The number of tablets;
- The patient ID number (e.g. ATB-YYY, where the study number and sequence number represent the unique patient identifier assigned at registration);
- The patient's initials (i.e., first, middle, last);
- A blank line for the site pharmacist to enter the patient's name;
- Administration instructions (i.e., "Take XX tablets every day for XX days");
- Storage instructions (i.e., "Store at controlled room temperature, XX degrees");

- Emergency contact instructions.

5.3 Storage and stability

The intact bottles should be stored at controlled room temperature (15°C – 30°C). Shelf life surveillance studies of the intact bottle are ongoing. Key active ingredients of ATB will be tested at regular intervals (every 3-6 months) to allow shelf life extension. Current data indicate ATB is stable at 90 days without decrement of active components at controlled room temperature (15°C – 30°C). Placebo tablets should be stored in the same way as ATB.

5.4 Accountability

The investigator, or a responsible party designated by the investigator, must maintain a careful record of the inventory and disposition of all agents. It is the responsibility of the investigator to ensure that the agents are only dispensed to study patients.

5.5 Drug Destruction

Opened bottles of ATB must be disposed of by incineration at the site as chemotherapy or biohazardous waste. At the completion of the study, all unused ATB also must be incinerated at the site. It is the responsibility of the investigator to ensure that a current record of agent disposition is maintained at each study site where agents are inventoried and disposed, including dates and quantities.

5.6 Biopsy specimen, Operative Specimen, and Tissue Processing

Baseline tumor specimens will be analyzed for Ki67 and ATB accumulation and stored for tissue banking for future research. For ATB accumulation studies, tumor and peritumor samples (>150 mg each per patient) should be snap frozen in liquid N2 and stored at -80C freezer until it is shipped. **The samples for ATB accumulation studies should not be fixed in formalin.** Submission of a block is preferred and is highly encouraged. If a block is not available, please provide at least five unstained slides. The block (or unstained slides) should be hand delivered to the CRI Histology Core (address below): The contact person is [name] ([contact]). Enrollment may proceed prior to receipt of outside biopsy specimen if it can be confirmed that there is sufficient tissue and sample will be released.

A portion of the OR-resected tumor will serve as post treatment specimen for comparison to the pre-treatment biopsy. At the time of surgery, a portion of the resected tumor will be utilized for the study. When possible, separate the tumors from the surrounding peritumor tissue. The specimen (i.e., tumor and peritumor) (minimum of 150 mg each) should be fresh frozen in liquid N2 and then stored in -80C freezer **without** formalin fixing. Any remnant tissue will be stored for further testing of biological correlates as mandated by the protocol.

The resected tumor will be received and processed by the MCW Tissue Bank staff. The tissue will be fixed in 10% buffered formalin as soon as resected, grossed into cassettes and processed into paraffin blocks. Once the blocks are in paraffin, they will be delivered to the CRI Histology Core for Ki67 testing. The paraffin block of the resected tumor and biopsy should be delivered to the following location:

[name]

Wisconsin Diagnostics Laboratories

[name]
Milwaukee, WI 53226

Immune response biomarker assessment (such as multiplex immunofluorescent staining) will be performed on biospecimens. Additional immune response testing will be performed based on initial results.

5.7 Dose Modifications

As indicated in the study calendar, a complete metabolic panel (including LFTs) will be performed midway during the course of ATB. Adverse events will be graded according to CTCAE v.5.

| Adverse Event (CTCAE, v. 5) | Action |
|---|---|
| Non-hematological, grade 1 or 2 | Continue ATB therapy at full dose prescribed. Apply maximum supportive care recommendations. If persistent duration of grade 2 adverse event is affecting quality of life, a one-time decrease of 25%. |
| Non-hematological, grade 3 or 4 | Apply maximum supportive care recommendations. Hold ATB therapy until recovery to grade ≤ 1 (up to 14 days). If concomitant elevation of AST/ALT 3 times the upper limit of normal and bilirubin elevation two times the upper limit of normal (Hy's Law criteria) the patient must be removed from study treatment, ATB must be permanently discontinued. If recurrence of adverse event after drug hold and/or interruptions is observed and maximum supportive care measures applied, a dose reduction by 25% is recommended. |
| Non-hematological, grade 3 or 4 and adverse events NOT resolved to grade ≤ 2 within a maximum of 14 calendar days from last planned administration | Dose reductions by 25% will be considered after maximum supportive care recommendations are introduced. |

| Dose Level | Dose |
|------------|-------------|
| -1 | 900 mg TID |
| 0 | 1200 mg TID |

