| Primary Objective | To determine the antiproliferative effects of ATB versus placebo as determined by tumor Ki-67. |
| Secondary Objectives | 
 1. Characterize the pharmacokinetics (PK) and pharmacodynamics (PD) properties 2. Determine the biologic correlates of response including NFkB, and RNASeq. |
| Primary Endpoint | Determine the anti-proliferative effects of ATB as determined by tumor Ki-67 in baseline tumor biopsy compared to resected control tumor tissue from untreated patients. |
| Secondary Endpoints | 
 1. PK and PD properties from the saliva samples collected during the period of the study will be calculated. 2. Measure biologic correlates of response including NFkB, and RNASeq from the tumor specimens collected at baseline and on the day of surgery. |
| Study Design | 
This is a window of opportunity study of ATB.
 
The study has been amended from a randomized study of ATB versus placebo to a single arm open label trial of ATB
 |

| | |
|---|--|
| | Upon initiating study treatment, patients will start taking the study drug. The duration of treatment will depend upon scheduling of their surgery—typically from the time surgery is scheduled it will be between seven to 28 days. Four (300 mg) pills will be taken three times per day until the evening prior to surgery. |
| Number of Subjects | Approximately *** subjects will be enrolled to achieve 14 total ATB-treated patients. |
| Estimated Time to Complete Enrollment: | Approximately two years. |

STUDY SCHEMA

STUDY CALENDAR:

| Procedure | Screening ¹ | ATB Administration: (Daily until Day -1 of Surgery) | | End of Treatment | |
|---|--|--|------------------------------------|------------------|-------------------------|
| Study Day/Visit Day | Day – 28 to Enrollment | Day 1 | Prior to Surgery ^{12, 13} | Day of Surgery | Follow Up ¹³ |
| Informed Consent | X | | | | |
| AE Reporting | Recorded from day 1 of the study drug through 30 days after the last dose of study drug (Section 6). | | | | |
| Concomitant Medications ³ | Recorded from signing of the ICF through 30 days after the last dose of study drug. | | | | |
| Physical Exam ² | X | | | X | X |
| Medical History ² | X | | | | |
| Pregnancy Test (Serum or Urine) ^{4, 13} | X | | | | |
| ECOG Performance Status ⁵ | X | | | | |
| Vital Signs per institutional standards | X | | | | |
| Complete metabolic panel ^{6,13} | X | | X | | X |

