| CBC w/ Diff and platelet count ¹³ | X | | X | | |
| PT, INR ¹³ | | | X | | |
| Research saliva samples ⁷ | | See footnote 7 for research saliva sample draw timepoints. | | | |
| Tumor Measurement by Physical Exam | X | | | | |
| Tumor Specimen ⁹ | X | | | X ⁸ | |
| CT ^{9, 8} | X | | X | | |
| MDASI-HN (MD Anderson Symptom Inventory-Head and Neck Survey) ¹³ | | X | X | | |
| ATB administration | | Patient to take as directed from day 1-prior to surgery | | | |
| Patient Diary ¹¹ | | X | X | | |

1. Screening procedures must occur within 28 days prior to registration. ATB administration should start within seven days of registration.
2. Focused physical examination by a study investigator.
3. Capture medications taken from signing of informed consent document until 30 days post last dose of ATB. Medications given during the surgical hospitalization will only be collected if related to Adverse event treatment.
4. For women of childbearing potential.
5. Refer to Appendix 1.
6. Including albumin, total protein, total bilirubin, direct bilirubin, ALT, AST, LDH, alkaline phosphatase, bicarbonate, sodium, potassium, chloride, creatinine, , calcium, BUN, and glucose.
7. A total of at least two patient samples (saliva) per day will be collected (predose, before lunch, or before dinner dose 1, dose 2, dose 3 of study drug). Saliva samples will be collected in a 5-ml bio vial, time documented by the patient, then frozen and stored by the patient until collection (see Section 3.1 for more details).
8. Fresh frozen tumor specimen will be collected, see section 5.6 for processing.
9. CT at baseline may be performed within six weeks prior to study registration. CT at day -1 of surgery can have a window of - 3 days. If baseline tumor is not measurable by baseline imaging (eg due to dental artifact) then follow-up imaging is NOT required
10. Patient will complete study diary with all relevant information and will submit the diary to study coordinator on the day of surgery.
11. The date for follow-up assessment is at the discretion of the surgeon and will correspond with the first post-operative outpatient assessment.
12. The indicated assessment for this timepoint will be collected only once with a window of two days: Day -3 to Day 0 of surgery.

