9.8 Investigator Compliance

The investigator will conduct the study in compliance with the protocol given approval/favorable opinion by the IRB and the appropriate regulatory authority(ies).

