10.5 Case Report Forms

The principal investigator and/or his/her designee will prepare and maintain adequate and accurate participant case histories with observations and data pertinent to the study. Study-specific case report forms (CRFs) will document safety and treatment outcomes for safety monitoring and data analysis. All study data will be entered into OnCore® via standardized CRFs, in accordance with the study calendar, using single data entry with a secure access account. The clinical research coordinator will complete the CRFs as soon as possible upon completion of the study visit; the investigator will review and approve the completed CRFs.

The information collected on CRFs shall be identical to that appearing in original source documents. Source documents will be found in the patient's medical records maintained by

MCWCC personnel. All source documentation should be kept in separate research folders for each patient.

In accordance with federal regulations, the investigator is responsible for the accuracy and authenticity of all clinical and laboratory data entered onto CRFs. The principal investigator will approve all completed CRFs to attest that the information contained on the CRFs is true and accurate.

All source documentation and data will be available for review/monitoring by the MCWCC DSMC and regulatory agencies.

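### Section 5.7 relies on a mid-course liver panel that the study calendar does not contain, so the Hy's Law stop may get its first input only in the last days before surgery

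*Combined protocol and SAP*

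**What the plan says.** Section 5.7 (Dose Modifications) states that "a complete metabolic panel (including LFTs) will be performed midway during the course of ATB" and presents this as something the study calendar already shows. The same section sets the liver rule: with transaminases at three times and bilirubin at two times the upper limit of normal, "the patient must be removed from study treatment, ATB must be permanently discontinued". It also provides for holding ATB for up to 14 days after a grade 3 or 4 non-hematological event.

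The calendar has five columns: Screening, Day 1, Prior to Surgery, Day of Surgery and Follow Up. The panel row reads "Complete metabolic panel ^{6,13} | X | | X | | X", that is, Screening, Prior to Surgery and Follow Up. Footnote 6 defines the panel: "Including albumin, total protein, total bilirubin, direct bilirubin, ALT, AST, LDH, alkaline phosphatase" and further analytes. Footnote 12, attached to the Prior to Surgery column, says: "The indicated assessment for this timepoint will be collected only once with a window of two days: Day -3 to Day 0 of surgery".

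Two other provisions bear on which text would prevail. Section 9.8 says "The investigator will conduct the study in compliance with the protocol", and section 5.7 is part of the protocol. Section 10.5 says "All study data will be entered into OnCore® via standardized CRFs, in accordance with the study calendar".

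**The concern.** Two operative parts of the plan disagree on whether chemistry is checked during dosing. Nothing in the documents suggests a decision to drop the mid-course draw: section 5.7 still orders it and believes the calendar carries it.

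The metabolic panel is the only calendar row that supplies AST, ALT and bilirubin. Without a mid-course draw, the first on-treatment values arrive just before surgery, when dosing is about to end anyway. The mandatory Hy's Law discontinuation, and any hold triggered by a laboratory value alone, could then prevent little exposure. The study-wide suspension in section 8.5, for drug-related toxicity of grade 3 or higher, would also learn late of an event visible only in the laboratory.

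What is at stake is the safety monitoring of individual patients. The primary endpoint and its analysis are not affected.

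**Working it through.** The plan gives no figure to reproduce, so the check compares the two texts and then counts dosing days.

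**Comparison.** Section 5.7 requires a panel midway. The calendar has no column between Day 1 and Prior to Surgery, and the panel's Day 1 cell is blank. The header and the panel row both have five cells, so a column lost in text extraction is unlikely. No other section schedules liver tests during dosing.

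**Inputs.**
- Course length L: 7 to 28 dosing days (sections 3.1 and 5.1).
- Three doses a day, the last on the evening before surgery (section 3.1), so Day -1 is dosing day L and Day -3 is dosing day L − 2.
- Calendar draw: once, Day -3 to Day 0 (footnote 12).
- Midpoint: ceil(L/2).

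The documents give no distribution of course lengths, so the range is shown.

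| | L = 7 | L = 14 | L = 21 | L = 28 |
|---|---|---|---|---|
| Midpoint, ceil(L/2) | day 4 | day 7 | day 11 | day 14 |
| Earliest calendar draw, L − 2 | day 5 | day 12 | day 19 | day 26 |
| Delay, (L − 2) − midpoint | 1 day | 5 days | 8 days | 12 days |
| Delay in doses (× 3) | 3 | 15 | 24 | 36 |
| Spared after midpoint draw, (L − midpoint)/L | 3/7 = 43% | 7/14 = 50% | 10/21 = 48% | 14/28 = 50% |
| Spared after Day -3 draw, 2/L | 2/7 = 29% | 2/14 = 14% | 2/21 = 10% | 2/28 = 7% |
| Spared after Day -1 or Day 0 draw | 0% | 0% | 0% | 0% |

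The shares assume that the draw day's doses are taken and that dosing stops afterwards. If the draw day's doses are also withheld, one day is added throughout. A Day -3 draw then spares 3 days (9 doses): 3/7 = 43%, 3/14 = 21%, 3/21 = 14%, 3/28 = 11%. A midpoint draw spares 4/7 = 57%, 8/14 = 57%, 11/21 = 52%, 15/28 = 54%. The contrast remains under either convention.

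**Longest gap between panels under the calendar.** Screening tests may be 28 days before registration, and dosing should start within 7 days after it. In a 28-day course, Day -3 is 25 days after the first dose. The gap can reach 28 + 7 + 25 = 60 days, or 63 for a Day 0 draw.

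**Does a midpoint draw make the 14-day hold workable?** Hardly. Counting the draw day, 4, 8, 11 and 15 dosing days remain. After a 14-day hold, one day is left (15 − 14), and only in a 28-day course with the hold starting on the draw day. The gain is earlier stopping, not hold and restart.

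**The case against.** The strongest reply is that the safeguard is already in the protocol. Section 5.7 orders the draw beside the Hy's Law rule, and section 9.8 binds the investigator to it, so harm follows only if staff overlook an express instruction. No text gives the calendar precedence, and section 10.5 concerns data entry, not the scheduling of blood draws. This stands in part: that the calendar would drive practice is an inference, and every figure above is conditional on it. But staff cannot satisfy section 5.7 from the calendar it cites, and there is no calendar timepoint against which to record the result.

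The calendar's footnotes are also imperfect. The diary row cites 11 while its text is at 10, and footnote 12 calls Day -3 to Day 0 two days. Footnote 12's wording still fits the Prior to Surgery column, and on any reading no mid-course panel is marked.

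The spared shares are best cases. They assume that the rise is already present at the draw and that the result is acted on by the end of that day. That is correct and limits what the numbers mean: they measure opportunity to stop, not risk.

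The expected harm is low. The largest earlier study (24,275 patients) mentions jaundice only as an unquantified, small number of cases. A six-month study with 300 participants on ATB reported no liver side effects. Both reports are qualitative. Exposure here is capped at 28 days, and severe active liver disease is excluded. Symptomatic events can surface through the diary and the twice-weekly coordinator contact. Against this, entry permits AST or ALT up to three times and bilirubin just under twice the upper limit, at or close to the Hy's Law thresholds. These points moderate the severity without resolving the conflict.

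**Conclusion.** The concern holds: section 5.7 and the study calendar contradict each other on the laboratory input to a mandatory stopping rule. If the calendar governs and the rise causes no symptoms, the first on-treatment result comes 1 to 12 days later than a midpoint draw, even on the earliest permitted day. Stopping after that Day -3 draw spares 7% to 29% of the course instead of 43% to 50%, and a Day -1 or Day 0 draw spares nothing. The 28-day figures are the upper bound, and the difference for a 7-day course with a Day -3 draw is one day.

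This should be fixed, but it is not evidence of liver toxicity. The contradiction itself is certain. Its practical consequence depends on how staff schedule the draws, which the documents do not settle.

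**What to change.** Add a mid-course column to the study calendar and mark the metabolic panel there. Set it at the midpoint of the planned course, counted from the surgery date scheduled at Day 1, with a window of plus or minus one day. Keep the pre-surgery panel. In a 7-day course, dosing day 5 is both midpoint plus one and Day -3, so one draw can serve both. Extend footnote 13 to this draw. It now allows community laboratories only in special cases with study team approval, and the calendar has no visit between Day 1 and Prior to Surgery.

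The cost is an IRB-approved amendment (section 9.7), some patient travel, and one draw per newly enrolled patient that section 5.7 already requires. The number of draws is not fixed by the documents: the enrolment figure is left as asterisks and the target is 14 ATB-treated patients. Assuming none has yet been treated and 0% to 20% are replaced under section 7.3, it is 14 to 18 draws (14/0.80 = 17.5, rounded up). Each patient already treated with ATB lowers it.

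Second best, if the sponsor intends the calendar schedule: delete the mid-course sentence from section 5.7 and state that on-treatment chemistry is checked only before surgery. That removes the contradiction but leaves the Hy's Law stop without timely input.
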